20.1 Visits

20.1.1 Visit 1, Screening (up to 14 days prior to the Baseline Visit)

The purpose of the screening visit is to inform the subject about the trial and to verify that the potentially eligible subject fulfills the inclusion criteria for the trial and do not meet any exclusion criteria. The screening visit should be performed within 14 days prior to the Baseline Visit. The informed consent must be signed prior to any screening assessments.

The following assessments will be performed:

- Informed consent
- Demographics
- Medical and surgical history
- Inclusion/exclusion criteria
- TB test (QFG-IT (Mantoux test can be used if QFG-IT is not possible))
- Physical examination
- Vital signs (supine blood pressure (BP) and heart rate)
- Body measurements (height and weight)
- Concomitant medication
- Concomitant therapy
- 12-lead ECG
- X-ray of chest, hands, and feet
- Blood samples (haematology, biochemistry and TSH, T3, and T4)
- Pregnancy test (serum)
- HBsAg, HBV antibody & HCV antibody
- Urinalysis (dipstick)
- RF or Anti-CCP
- CRP
- SJC and TJC
- CDAI
- Investigator Global VAS
- Patient Global VAS

Protocol Code Number: SynAct-CS002

Patient Pain VAS

20.1.2 Visit 2, the Baseline Visit (Day 0)

The subject will come back to the hospital for the Baseline Visit. Inclusion and exclusion criteria will be confirmed. If the subject is still eligible for participation, the subject will be randomized. The following assessments will be performed:

- Check of inclusion/exclusion criteria
- Vital signs (supine BP and heart rate)
- Changes in concomitant medication
- Changes in concomitant therapy
- 12-lead ECG
- Blood samples (hematology, MC1R genotype analysis*, biochemistry and TSH, T3, and T4)
- CRP
- Cytokines
- Pregnancy dipstick test
- Body measurements (weight)
- Adverse event recording
- SJC and TJC
- CDAI
- Investigator Global VAS
- Patient Global VAS
- Patient Pain VAS
- FACIT-Fatigue
- DAS28
- HAQ-DI
- Randomization
- Dispensing of IMP
- * At baseline or any other visit after randomization

20.1.3 Visit 3, 1. Week treatment Visit

The 1. Week Treatment Visit, 7 days (±1 day) after the Baseline Visit. The following assessments will be performed:

- PK blood sample
- Blood samples (biochemistry and TSH, T3, and T4)
- Changes in concomitant medication
- Changes in concomitant therapy

Protocol Code Number: SynAct-CS002

- 12-lead ECG
- Pregnancy dipstick test
- Body measurements (weight)
- Adverse event recording
- Accountability of returned IMP and dispensing of new IMP

20.1.4 Visit 4, 2. Week treatment Visit

The 2. Week Treatment Visit, 14 days (±1 day) after the Baseline Visit. The following assessments will be performed:

- PK blood sample
- Vital signs (supine BP and heart rate)
- Changes in concomitant medication
- Changes in concomitant therapy
- 12-lead ECG
- Blood samples (hematology, biochemistry and TSH, T3, and T4)
- Cytokines
- CRP
- Pregnancy dipstick test
- Body measurements (weight)
- · Adverse event recording
- SJC and TJC
- CDAI
- Investigator Global VAS
- Patient Global VAS
- Patient Pain VAS
- FACIT-Fatigue
- DAS28
- Accountability of returned IMP and dispensing of new IMP

20.1.5 Visit 5, 3. Week treatment Visit

The 3. Week Treatment Visit, 21 days (±1 day) after the Baseline Visit. The following assessments will be performed:

- PK blood sample
- Blood samples (biochemistry and TSH, T3, and T4)
- Changes in concomitant medication
- Changes in concomitant therapy

Protocol Code Number: SynAct-CS002

- 12-lead ECG
- Pregnancy dipstick test
- Body measurements (weight)
- Adverse event recording
- Accountability of returned IMP and dispensing of new IMP

20.1.6 Visit 6, 4. Week treatment Visit

The 4. Week Treatment Visit 28 days (±1 day) after the Baseline Visit. The following assessments will be performed:

- PK blood sample
- Vital signs (supine BP and heart rate)
- Changes in concomitant medication
- Changes in concomitant therapy
- 12-lead ECG
- Blood samples (hematology, biochemistry and TSH, T3, and T4)
- CRP
- Cytokines
- Pregnancy dipstick test
- Body measurements (weight)
- · Adverse event recording
- SJC and TJC
- CDAI
- Investigator Global VAS
- Patient Global VAS
- Patient Pain VAS
- FACIT-Fatigue
- DAS28
- HAQ-DI
- Accountability of returned IMP

20.1.7 Visit 7, One-week post-treatment

The subject will return to the hospital for a final visit, 7 (±2 days) days after the last IMP has been taken. The following assessments will be performed:

- Pregnancy dipstick test
- Urinalysis (dipstick)
- Blood samples (hematology, biochemistry and TSH, T3, and T4)

Protocol Code Number: SynAct-CS002

- Vital signs (supine BP and heart rate)
- CRP
- Physical examination
- Body measurements (weight)
- · Adverse event recording
- Changes in concomitant medication
- Changes in concomitant therapy
- 12-lead ECG
- SJC and TJC
- CDAI
- Investigator Global VAS
- Patient Global VAS
- Patient Pain VAS
- FACIT-Fatigue
- DAS28
- HAQ-DI

20.1.8 Final safety Follow-up Call and EOS

Investigator or study nurse will call the subject 4 weeks after the subject took the last IMP to follow-up on outstanding safety issues (AE/SAE).

21 Assessments, procedures, and Examinations

Subjects must provide written informed consent before any study-related procedures are performed.

Subject-related events and activities including specific instructions, procedures, concomitant medications, dispensing of study drug, and descriptions of AEs should be recorded in the appropriate source documents and the eCRF.

The schedule of assessments is provided in a study flow chart (Table 3) and is listed in Section 205. Unless otherwise specified, the investigator or accredited study personnel will perform all assessments.

Extra visits, examinations, tests, and interventions can be performed at any time if clinically indicated, as judged by the investigator.

21.1 Safety Assessments

21.1.1 Medical History

A complete medical (and surgical) history of each subject will be collected and documented during screening to determine the subject's eligibility for the trial. The medical history will include, but may not be limited to, prior and current concomitant disease and treatments, including all previous and current therapies for RA.

Protocol Code Number: SynAct-CS002

Relevant medical history will be recorded in the eCRF and includes diagnosis and assessments of any current medical condition and concurrent health conditions.

21.1.2 Prior and Concomitant Medication

Prior medications/therapies will be reported if taken up to 4 weeks prior to the Screening Visit. Concomitant medications/therapies, herbal medication, and over-the-counter medication will be reported at every visit throughout the trial.

21.1.3 Pregnancy Test

For all females of childbearing potential, a serum pregnancy test will be performed at screening and at all the following visits the pregnancy test will be a urine dipstick test. In the event of pregnancy, the subject is not allowed to receive further study treatment and must be withdrawn from the study. The pregnancy must be reported to the sponsor on a Pregnancy form and followed until the end of pregnancy.

21.1.4 Physical Examination

A full physical examination (including examination of general appearance, skin, neck (including thyroid), eyes, ears, nose, throat, heart, lungs, abdomen, lymph nodes, musculoskeletal, cardiovascular, nervous systems, and joints) will be carried out by a physician at screening and at the final visit (Visit 7) or early withdrawal. Any clinically significant abnormalities at screening will be noted on the medical history pages of the eCRF. During the study, if in the opinion of the investigator there are any clinically significant changes in the physical examination findings (abnormalities), they will be recorded as AEs.

21.1.5 Height and Weight

Subject height will be measured at the Screening Visit, while weight will be assessed at all visits except at the visit 8 (EOS/Safety follow-up call).

21.1.6 Vital Signs

Vital signs will be collected for evaluation by the investigator. Reference values for the vital signs are presented in the table below. If any value is outside the reference range, the measurement will be repeated at the investigator's discretion, and the final measurement will be reported in the eCRF.

Table 4, Reference values for vital signs

Vital Sign Parameter	Range
Systolic blood pressure	90–140 mm Hg
Diastolic blood pressure	60–90 mm Hg
Heart rate (resting)	50–100 beats per minute (bpm)
Respiratory rate	12–20 breaths per minute

All vital sign values will be evaluated for clinically notable results as defined in Table 5, Any subject with a clinically notable vital sign abnormality will be immediately evaluated by qualified personnel to ensure that any required acute medical intervention or other appropriate supportive medical care is provided. All vital sign abnormalities, including clinically notable vital sign abnormalities, will be evaluated using appropriate medical

Protocol Code Number: SynAct-CS002

judgment to determine whether they represent AEs. Vital sign abnormalities that require medical intervention (beyond confirmatory vital sign collection) are to be regarded as AEs. Vital signs will be assessed at all visits.

Table 5, Criteria used to identify clinically notable vital sign abnormalities

Vital Sign Parameter	Value
Systolic blood pressure	≥ 160 mm Hg or < 90 mm Hg
Diastolic blood pressure	≥ 105 mm Hg or ≤ 50 mm Hg
Heart rate	≥ 120 bpm or < 40 bpm
Respiratory rate	< 12 breaths per minute or > 20 breaths per minute

21.1.6.1 Blood pressure, Heart, and Respiratory Rate

Blood pressure and pulse rate will be measured on the non-dominant arm after 5 minutes of supine rest. Blood pressure will be recorded in mmHg, heart rate will be measured in bpm and respiratory rate in breaths per minutes.

21.1.7 Lead Electrocardiographic Evaluation

A twelve (12) lead ECGs will be obtained on all subjects at every visit throughout the trial. The ECG should be performed after the subject has rested quietly for at least 10 minutes.

The following ECG parameters will be obtained from the digital 12-lead ECG recordings: rhythm, heart rate (as measured by RR interval), PR interval, QRS duration, and QT interval. The corrected QT interval (QTcF) will be calculated using Fridericia's formula $(QTc=QT/\sqrt[3]{RR})^{43}$ or by using CliniCalc: (https://www.clinigate.com/clinicalc/corrected-qt-interval-qtc.php)

The investigator must evaluate all ECGs as normal/abnormal and if abnormal as clinically significant or not clinically significant. The printout of the ECG should be signed and dated. The overall evaluation (normal/abnormal) will be recorded on the eCRF, and if abnormal, the specific abnormality will be recorded too.

Each print-out must include the following information: trial number, subject's screening number, date of birth, and date and time of recording. All reference to the subject's name and/or social security number must be erased from the print-out so that only the subject's screening number is used as identification.

21.1.8 X-ray

A chest x-ray (only at the Screening Visit) will be used to reveal active current or history of tuberculosis and atypical mycobacterial disease, clinically significant abnormalities on chest x-ray as determined by the investigator.

X-ray of hands and feet (only at the Screening Visit): radiographic changes typical of RA on posteroanterior hand and wrist x-rays.

If the subject has a chest x-ray and/or x-ray of hands and feet that are no older than 6 months the x-rays can be used for the evaluation.

Protocol Code Number: SynAct-CS002

The average radiation dose for adults is 60 microsievert (μ Sv) per x-ray image, which is a very shallow dose. In comparison, the average background radiation (i.e., the average radiation that an individual is exposed to per year from natural background radiation sources) is 1000 μ Sv. The radiation dose that a subject is exposed to is thus evaluated to be safe. Furthermore, the additional information, which such images can provide about radiographic changes typical for rheumatoid arthritis, is anticipated as valuable knowledge for the project.

21.1.9 Laboratory Assessments

The study sites will use local laboratories to perform standard hematology, biochemistry, and urine analyzes. Laboratory results will be evaluated by the investigator for inclusion and exclusion criteria. Also, the investigator will assess whether any values reflect AEs and if so, report them as described in section 18. The latest updated reference ranges from the local laboratory will be used to identify subjects with clinically notable laboratory values.

21.1.9.1 Hematology

Hemoglobin, white blood cell (WBC) count (total and differential: leukocytes, neutrophils, eosinophils, basophils, lymphocytes, monocytes), red blood cells (RBC), thrombocytes and hemoglobin A1c (HbA1C). The hematology blood samples will be taken at screening, baseline, after 2 weeks and 4 weeks treatment and Visit 7.

21.1.9.2 MC1R genotype analysis

The human melanocortin receptor type 1 (MC1R) is a highly polymorphic gene. It is known that some receptor variants are associated with loss of function when characterized by the receptor's ability to induce cAMP accumulation. There is evidence that the loss of function is restricted to the cAMP pathway, i.e., the ability to stimulate the ERK phosphorylation pathway, the pathway stimulated by AP1189, for most receptor variants are preserved.

At baseline or any other visit after randomization, a blood sample will be taken once to identify the MC1R variant in randomized patients.

The blood sample is stored at -80° in a research biobank until shipment and subsequent analysis at Statens Serum Institut (SSI). The genotype sequencing method is used in the blood sample analysis, meaning that only the gene variations that have to do with the melanocortin receptor are examined.

The company Genetelligence is responsible for the interpretation of the genetic tests, and the results are only used in the above study.

All blood samples will be destroyed after analysis, and no samples will be saved for future research.

21.1.9.3 Biochemistry

Sodium, potassium, chloride, calcium, glucose, creatinine, urea, albumin, unconjugated and total bilirubin, aspartate transaminase (AST), alanine transaminase (ALT), alkaline phosphatase (ALP), gamma-glutamyl transferase (GGT) and INR. The biochemistry blood samples will be taken at all visits. A serum β -HCG pregnancy test will be taken at screening (dipstick pregnancy test at all other visits).

Protocol Code Number: SynAct-CS002

21.1.9.4 Thyroid function

Thyroxine (T4) total or free, triiodothyronine (T3) total or free, and the thyroid-stimulating hormone (TSH). Blood samples for measuring the thyroid function will be taken at all visits.

21.1.9.5 Urinalysis

A dipstick urine test for blood, protein, and glucose will be performed at the site at the Screening Visit and Visit 7. If any of the results are abnormal and clinically significant, a urine sample will, at the discretion of the investigator, be sent for urine culture at the local laboratory.

21.1.9.6 Serology

RF or anti-CCP, HBsAg, HBV antibody and HCV antibody (only at screening).

RF is an antibody that is detectable in the blood of approximately 80% of adults with RA.

CRP is an acute phase reactant, a protein made by the liver and released into the blood within a few hours after tissue injury, the start of an infection, or other cause of inflammation. The CRP will most often be increased by inflammation. One of the aims of treatment is to reduce the CRP to normal levels. CRP will be measured at screening, baseline, after 2 weeks and 4 weeks treatment and at Visit 7.

21.1.9.7 Safety (AE and SAE)

Safety measures (AEs, SAEs, including laboratory abnormalities) will be registered during the whole study duration.

21.2 Safety Assessments (Sub-study, only Part 2)

The arthroscopy sub-study in Part 2 (only at selected sites), will assess the effect of 4 weeks treatment with AP1189/placebo compared to baseline by examining synovial fluid: (evaluating the change in the percentage of polymorphs, monocytes, and lymphocytes in synovial fluid).

In RA the immunohistological features of synovial inflammation change as the clinical manifestations change in response to conventional disease-modifying antirheumatic drugs, pulse methylprednisolone, or intra-articular glucocorticoids^{45, 45, 46, 47, 48, 49, 50, 51}. These observations from many clinicopathological research protocols have provided compelling evidence to support the inclusion of synovial biopsy and tissue analysis in studies of the cause, pathogenesis, prognosis, and effects of treatment⁵².

21.3 Efficacy Assessments

The following tests and procedures have been selected to evaluate the efficacy of AP1189 and to describe the clinical improvement in subjects with RA. The tests and procedures will be performed according to the Study Flow Chart in section 18, Table 3.

21.3.1 Swollen Joint Count (SJC) and Tender Joint Count (TJC)

An assessment of 66 joints for swelling and 68 joints for tenderness will be made at screening, baseline, after 2 weeks and 4 weeks treatment and Visit 7. Joints will be assessed and classified as swollen/not swollen and tender/not tender by pressure and joint manipulation on physical examination. The subject will be asked for pain sensations on these manipulations and watched for spontaneous pain reactions. Any positive response to pressure, movement, or both will then be categorized as tender-versus-nontender. Swelling is defined as

Protocol Code Number: SynAct-CS002

palpable fluctuating synovitis of the joint. Swelling secondary to osteoarthrosis will be assessed as not swollen unless there is unmistakable fluctuation.

Joint assessments of one particular subject should be performed by the same assessor (if at all possible) throughout the trial to minimize inter-observer variation.

21.3.2 Clinical Disease Activity Index (CDAI)

The CDAI is a useful clinical composite score for following patients with RA. Descriptive changes in CDAI where CDAI = SJC (28) + TJC (28) + PGA + IGA

- SJC (28): Swollen 28-Joint Count (shoulders, elbows, wrists, MCPs, PIPs including thumb IP, knees)
- TJC (28): Tender 28-Joint Count (shoulders, elbows, wrists, MCPs, PIPs including thumb IP, knees)
- PGA: Patient Global Disease Activity (patient's self-assessment of overall RA disease activity on a scale 0-100 where 100 is maximal activity)
- IGA: Physician's Global Disease Activity (evaluator's assessment of the subject's overall RA disease activity on a scale 0-100 where 100 is maximal activity)

The CDAI will be scored at screening, baseline, after 2 weeks and 4 weeks treatment and at Visit 7.

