16.2 Inclusion Criteria

Subject eligibility should be reviewed and documented by an appropriately qualified member of the investigator's study team before subjects are included in the study. The following are requirements for entry into the study.

- 1. Written informed consent has been obtained prior to initiating any study specific procedures
- 2. Male and female subjects, 18 to 85 years of age
- 3. Confirmed diagnosis of RA according to the 2010 ACR/EULAR RA classification criteria
- 4. Arthritis with joint swelling and tenderness of a minimum of three joints out of 68 joints tested
- 5. Candidate for MTX treatment
- 6. Is about to begin treatment with MTX
- 7. Tested positive for anti-CCP or RF
- 8. Severe active RA (CDAI > 22) at screening and baseline
- 9. Negative QFG-IT (Mantoux test can be used if QFG-IT is not possible)
- 10. Subjects should be able to complete (read and write) the PRO questionnaires
- 11. Females of child-bearing potential may only participate if using reliable means of contraception (for detailed information see section 17.8) or are post-menopausal (menstrual periods stopped at least 12

Protocol Code Number: SynAct-CS002

months ahead of the enrolment in the trial). Surgically sterilized women at least 6 months prior to screening

12. Females of childbearing potential must have a negative pregnancy test at screening and baseline.

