## 3.7 Interim Analysis

An interim analysis has been performed, evaluating the first (minimum) 24 subjects from Part 1 of the trial in order to assess the safety and efficacy of the investigational product before proceeding to Part 2. Version 1 of this analysis plan was used for the interim analysis.

All safety parameters (ECG, vital signs, AEs/SAEs, laboratory abnormalities, etc.) and efficacy data for the primary efficacy endpoint were summarized by treatment and time point for the subjects included in Part 1 of the study, i.e., the following tables (see Appendix 4 for details) were presented (any MedDRA coding of AEs will not be performed for the interim):

• Table 11.4.1.3 (CDAI score)

Study SynAct-CS002 – Statistical Analysis Plan

- Table 11.4.1.4 (CDAI score, change from baseline to week 4)
- $\circ~$  Table 11.4.1.5 (CDAI score, change from severe (CDAI > 22) to moderate (CDAI  $\leq$  22) at week 4 compared to baseline)
- Table 12.2.1.1 to Table 12.5.5.1 (all safety tables).

Listings showing the following data were also presented:

- Patient disposition (including end of study information), i.e., the following listings (see Appendix 4 for details):
  - Listing 6.4.1 (Visit Registration)
  - Listing 6.4.2 (Informed Consent, Randomization, Subject Summary)
  - Listing 6.4.3 (Alcohol Consumption)
  - Listing 16.2.8.1 TB and Serology Tests)
  - Listing 6.4.10 (Inclusion Exclusion Criteria)
- Demographics and baseline characteristics, i.e. the following listings (see Appendix 4 for details):
  - Listing 16.2.4.1 (Demographics)
  - Listing 6.4.5 (Vital Signs)
  - Listing 16.2.4.3 (Age)
- Safety profiles (laboratory values, adverse events, related adverse events, serious adverse events (SAE), adverse events leading to withdrawal), i.e., the following listings (see Appendix 4 for details):
  - Listing 16.2.8.2 (Blood Biochemistry)
  - Listing 16.2.8.3 (Blood Haematology)
  - Listing 16.2.7.1 (Adverse Event Q).
- Efficacy data for the primary study endpoint
  - Listing 16.2.6.3 (CDAI)
  - Listing 16.2.6.7 (Changes from baseline in CDAI)

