An independent external statistician conducted the interim analysis. The external statistician is included in the Data Monitoring Committee (DMC) established by the sponsor. The DMC reviewed the unblinded data from the interim analysis and recommended one of the three study designs for Part 2 to the Steering Committee. The criteria for choice of design are described in the Data Monitoring Committee Charter (Appendix 3). All recommendations are documented and signed by the DMC members, and they provided a summary of the safety and tolerability data obtained in Part 1 and their design recommendation for Part 2.

The independent external statistician will ensure that the interim analysis is a completely confidential process. Sponsor, investigators, and other study personnel will be kept blind. The Steering Committee's final decision on design choices for Part 2 of the study was communicated to all investigators and study personnel as soon as the decision was made.

At the end of the study, any discrepancies between the final and the interim data, which could significantly impact the analysis, should be documented.

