### 3.12 Documentation and Other Considerations

Protocol Section 12.2 Primary efficacy Objective states "Effect of AP1189 vs. placebo in subjects with severe active RA (CDAI > 22), undergoing up-titration with MTX, by showing a change in CDAI from severe (CDAI > 22) to moderate (CDAI  $\leq$  22) after 4 weeks treatment compared to baseline." The cut-off values for the CDAI score correspond to severe (CDAI>22) or moderate **or lower** (CDAI  $\leq$  22), which is the wording used in this analysis plan.

Protocol Section *12.3 Secondary efficacy Objectives* states that the "Proportion of subjects achieving American College of Rheumatology (ACR) response assessed by ACR20, ACR50, and ACR70" will be assessed. These responses will be assessed at week 4 compared with baseline (no time point was specified in the protocol).

Protocol Section 12.4 Tertiary Efficacy Objectives states that the "Effect of AP1189 compared to placebo at week 4 compared to baseline on inflammatory and collagen destructive biomarkers" will be assessed. The comparison to baseline will be made by calculating the change for these biomarkers (CXCL13, IL-1 $\beta$ , IL-6, IL-10, and TNF- $\alpha$ ) at week 4 compared with baseline (the calculation of a change from baseline was not specified in the protocol). In addition, the ratio IL-6/IL-10 will be evaluated in the same way.

Protocol Section 23.6 Pharmacokinetic Analyses states that "Descriptive statistics will be used for an exploratory description of exposure in relation to effect." However, only one sample is taken at each visit (for some visits), with variability in the time from last dosing to sampling. Thus, the relationship between exposure and effect is not possible to evaluate, and exposure will therefore be described without relation to effect..

No other changes to analyses specified in the protocol have been identified at the time of writing this SAP.

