#### 6.1.1 Description of primary efficacy variables

| Variable (CRF annotation)   | How to be presented                                    |
|---|--|
| Patient Global Assessment of Disease Activity RA,
cm (PGADA, dataset CDAI)                                   | n, mean (95% CI), sd, median, min, max, by
visit    |
| Patient Global Assessment of Disease Activity RA,
cm, relative to placebo (derived, see Section 3.6)         | Mean, median, min, max, by visit, country, and site    |
| Investigator Global Assessment of Disease
Activity RA, cm (IGADA, dataset CDAI)                              | n, mean (95% CI), sd, median, min, max, by
visit    |
| Investigator Global Assessment of Disease
Activity RA, cm, relative to placebo (derived, see
Section 3.6) | mean, median, min, max, by visit, country,
and site |
| CDAI score calculated (CDAI)  | n, mean (95% CI), sd, median, min, max, by visit       |

Study SynAct-CS002 – Statistical Analysis Plan

| CDAI score calculated, relative to placebo (derived, see Section 3.6)  | Mean, median, min, max, by visit, country, and site          |
|--|--|
| CDAI change from baseline to week 4 (derived, see Section 3.6)   | n, mean (95% CI), sd, median, min, max, by
visit          |
| Proportion of subjects with a change in CDAI
score from severe (CDAI > 22) to moderate or
lower (CDAI ≤ 22) at week 4 compared to
baseline (derived, see Section 3.6) | <pre># patients and % /category (2 categories: Yes/No)</pre> |

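### The protocol's CDAI formula uses 0-100 global scores, the SAP holds the same globals in cm, and nothing says which scale the cut-off of 22 belongs to

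*Protocol*

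**What the plan says.** Protocol 21.3.2 holds the only CDAI formula in either document: SJC28 + TJC28 + PGA + IGA. PGA is "patient's self-assessment of overall RA disease activity on a scale 0-100 where 100 is maximal activity" and IGA is "evaluator's assessment of the subject's overall RA disease activity on a scale 0-100 where 100 is maximal activity". No division is applied to either. Protocol 21.3.4 and 21.3.5 collect both globals on a 100 mm line.

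SAP 6.1.1 lists the patient global as "cm (PGADA, dataset CDAI"), gives the investigator global in the same unit and dataset, and in the same table lists "CDAI score calculated (CDAI") as a CRF field. SAP 2.1.4 sends the reader to section 3.6 for the calculation. Section 3.6 has change scores, point-decrease indicators and cut-offs of 22, 10 and 2.8, but no CDAI formula, and its conversion table covers only QTc and laboratory values. SAP 3.12 discusses the cut-off of 22 only to add that a score at or below it means moderate or lower, and ends: "No other changes to analyses specified in the protocol have been identified at the time of writing this SAP".

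The cut-off is used twice. Protocol 16.2 requires "Severe active RA (CDAI > 22) at screening and baseline", and the primary responder variable is a move from above 22 to 22 or below at week 4.

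**The concern.** A fixed threshold means something only on a stated scale. Two programmers, one following the protocol formula and the other summing the SAP's cm fields, would obtain different eligible populations and different primary results from the same case report forms.

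The scale carries through to both primary efficacy variables (mean change and responder proportion), every point-decrease indicator, and the 10 and 2.8 cut-offs. It also reaches the interim analysis. SAP 3.7 lists "Table 11.4.1.4 (CDAI score, change from baseline to week 4") and the matching responder table, 11.4.1.5, among the outputs, and Protocol 15.10 bases the Part 2 design partly on the number of subjects with a reduced clinical score.

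**Working it through.** **Inputs.** Formula and 0-100 globals: Protocol 21.3.2. Globals in cm: SAP 6.1.1. Cut-off of 22: Protocol 16.2 and SAP 3.6. A 100 mm line read in cm runs 0-10, so cm = mm / 10. The patient values below are assumed for illustration.

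**Range of the score**
- Protocol: 28 + 28 + 100 + 100 = 256
- Cm: 28 + 28 + 10 + 10 = 76

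**Individual scores**

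| Patient | Protocol formula | Cm |
|---|---|---|
| Entry: 3 + 3 joints, globals 50 and 50 mm | 3+3+50+50 = 106, eligible | 3+3+5+5 = 16.0, not eligible |
| Baseline: 8 + 8 joints, globals 60 and 60 mm | 8+8+60+60 = 136, eligible | 8+8+6+6 = 28.0, eligible |
| Same patient at week 4: 3 + 3 joints, globals 20 and 20 mm | 3+3+20+20 = 46, non-responder | 3+3+2+2 = 10.0, responder |
| Change from baseline, same patient | 46 - 136 = -90 | 10.0 - 28.0 = -18.0 |

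**What the cut-off demands.** With 3 + 3 joints, 22 - 6 = 16 points are left for the two globals. CDAI of 22 or below then needs the globals to total at most 16 mm by the protocol formula, or at most 16 cm = 160 mm on the cm scale. Entry is the mirror image: above 16 mm, or above 160 mm. At the extreme, two globals of 12 mm give 24 by the protocol formula with no swollen or tender joint at all. In cm they add 2.4, so at least 20 joint points are needed to pass 22.

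**Point decreases.** A 5-point fall from one global alone takes 5 mm by the protocol formula and 50 mm in cm.

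**Does the sample size reveal the scale?** The plan's figure reproduces. Width = 2 × t(0.975, n-1) × SD/√n × √(χ²(0.80, n-1)/(n-1)). With n = 25 and SD = 3 this is 2.75 (stated: about 2.8); with n = 30 it is 2.47 (stated: about 2.5). The arithmetic is sound, but the scale of the SD is not named.

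The documents give no component SDs, so I assumed an SD of change of 2-3 points for the joint part, 1-2 cm for each global, a correlation of 0-0.5 between the globals, and independence from the joint part. The SD of the total is then √(SD_joint² + 2·SD_global²·(1+ρ)):
- globals in cm: 2.4 to 4.6
- globals on 0-100: 14 to 35

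At n = 25 the interval widths are 2.2-4.2 and 13-32 points respectively. A planning SD of 3 fits the cm scale much better.

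**The case against.** The best defence is that the trial plainly worked in cm and the protocol sentence merely lacks a division by 10. The SAP places the cm globals in the CDAI dataset beside the calculated score, and SAP 6.1.2 names the re-entered 28-joint counts as used for the CDAI calculation. A remission cut-off of 2.8 is not a whole number, and the planning SD of 3 is hard to square with 0-100 globals. On this view one formula line is missing and the harmful case is unlikely. Misclassification also depends on patient values: the baseline example above is eligible on either scale. Moreover, SAP 8.4 calls for recalculation of at least 20% of calculated efficacy data.

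Much of this stands as inference. Cm is the likelier scale, and nothing here shows that the collected data are wrong. But no passage ties 22 to cm, and the annotated CRF and SAP Appendix 4 are not among the documents reviewed. The only written formula contradicts the inference. A recalculation check cannot settle the scale when the SAP has no formula to recalculate from.

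**Conclusion.** The point holds. The protocol's definition of its entry score and primary efficacy score is contradicted by the SAP's units, and the SAP neither resolves nor records the difference. The conflict is a factor of 10 on two of the four components, enough to reverse eligibility (106 against 16.0) and response (46 against 10.0) at the same cut-off.

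The consequence depends on the eCRF. If its CDAI field used cm throughout, the data are consistent and the protocol text needs correcting. If it followed Protocol 21.3.2, eligibility, the primary responder variable and the interim CDAI tables are affected. Either way a correction is needed before the primary analysis. Confidence is high for the textual conflict; which branch applies cannot be settled from these documents.

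**What to change.** 1. Confirm which scale the eCRF CDAI field used for eligibility, the interim analysis and the endpoints.
2. Reconcile Protocol 21.3.2 with the SAP by stating one unit for both globals: cm (mm divided by 10), if step 1 confirms it.
3. Write the formula in SAP 3.6 with field names (the re-entered 28-joint counts, plus PGADA and IGADA from the CDAI dataset), state the scale for the cut-offs and point decreases, and list the change in SAP 3.12.
4. Before unblinding, recompute CDAI centrally from its components. Flag subjects not above 22 at screening or baseline as deviations for the per-protocol set. Handle any difference from the interim under SAP 3.7, which says that "any discrepancies between the final and the interim data, which could significantly impact the analysis, should be documented".
5. While editing, state that the patient global enters DAS28 in mm (Protocol 21.3.3), so a value held in cm (SAP 6.1.4) is multiplied by 10. No passage directs otherwise; this only closes the same gap.

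**Cost.** If the eCRF used cm throughout: one protocol sentence, two SAP lines and a check against the collected data. If it followed the protocol formula: also a re-check of Part 1 eligibility and of the interim CDAI tables.
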